4.2.10 Intervention Fidelity Assessment

Peers will maintain logs of contact with participants randomized to the intervention arm. Peers will submit weekly logs of participant contact to site study research program coordinators.

4.2.11 Assessment of implementation outcomes

The well validated Reach, Effectiveness, Adoption, Implementation, and Maintenance (RE-AIM) framework²⁰ will be used to guide evaluation of implementation outcomes of peer enhanced HCV treatment at OTP sites using its dimensions; reach and effectiveness, which operate at the individual level of those intended to benefit; and adoption and implementation which focus on staff and setting levels. We will focus on acceptability of the peer enhanced drug treatment center based HCV test and treat strategy, barriers and facilitators of implementation success and congruence with drug treatment

clinic workflow. In-depth interviews will focus on exploring how peer supported drug treatment clinic based HCV treatment may become embedded in routine clinical practice in drug treatment settings. We will utilize a mixed methods assessment including quantitative survey data from patients (collected through clinical trial), and qualitative in-depth interviews (IDI) with drug treatment clinic leadership and staff (n=45) and program peers (n=15) across five sites.

Setting and population: The focus of this assessment is individuals implementing and being affected by implementation of peer-supported drug treatment clinic based HCV treatment. We will utilize the RE-AIM framework for this assessment.

Table 1: Summary of Implementation Outcomes Using the RE-AIM Framework

Component	Research Question	Assessment Method(s)	Outcome(s) of Interest	Sampling of qualitative interview content
Reach	Who received the peer enhanced drug treatment center based HCV test and treat intervention?	Study data Patient in depth interviews (IDI)	
 • Proportion of study participants who initiated HCV treatment. • Characteristics of those who initiated vs. those who did not initiate HCV treatment 	Barriers and facilitators to HCV treatment initiation What components of the intervention were most effective (patients)
Effectiveness	What impact did the intervention have on outcomes?	HCV treatment initiation (Study data)	
 • Proportion of study participants who initiated HCV treatment in intervention compared to SOC arm. 	--
Adoption	Did the patients, peers and drug treatment center adopt the intervention?	Study data, peer contact logs, OTP staff and peer surveys, IDI with providers, staff, peers	
 • Frequency of contacts between peers and patients. • Proportion of patients who previously failed to and subsequently cross over and initiate HCV treatment 	Barriers and facilitators to adoption (intervention uptake), steps to enhance uptake; perceived need for intervention, perceived fit in current care structure (peers, drug treatment clinic staff, clinic leadership)
Implementation	Was the intervention	Standardized fidelity	
 • Adherence to intervention protocols (Fidelity) 	Perceptions of the most effective components of the

	delivered as intended?	assessment form, IDI	
 • Dose frequency of peer contact with patient. • Frequency of HCV medication pick-up at OTP 	intervention (peers, providers, clinic staff, leaders),
--	------------------------	----------------------	--	--

4.2.12 Adjustments for COVID related restrictions

Study specific activities including screening, consenting, survey administration will have the option of being performed remotely by phone or video visits with research staff. All study activities that must be done in-person (sample collection, study medication dispensation) for participants in both arms may occur during the participant's regularly scheduled OTP visits. No additional research-only visits to OTP will be needed.

5 STUDY ACTIVITIES

5.1 Inclusion and exclusion Criteria

Inclusion criteria: Participants must meet all of the following inclusion criteria to be eligible for participation

- ✓ Ability and willingness of participant to provide written informed consent
- ✓ Men and women age ≥ 18 to ≤ 70 years at study entry
- ✓ HCV antibody positive/Detectable HCV RNA
- ✓ HCV treatment naïve (no prior treatment with an approved or investigational oral DAA therapy)
- ✓ Negative pregnancy test at screening or at the day of treatment initiation (females of childbearing potential only)
- ✓ If co-infection with Human Immunodeficiency Virus (HIV) is documented, the subject must be anti-retroviral treatment (ART) naïve with CD4 T cell count >500 cells/mm³ OR on a stable ART regimen (containing only permissible ART – Raltegravir; dolutegravir; Rilpivirine; Elvitegravir/cobicistat; Tenofovir disoproxil fumarate; Tenofovir alafenamide; Emtricitabine; Lamivudine and/or Abacavir, bicitegravir)

Exclusion criteria: Subjects who meet any of the following exclusion criteria are not to be enrolled in this study

- ✓ Women who are pregnant or breastfeeding, or considering becoming pregnant during the study and for 30 days after the last dose of study drug
- ✓ Known allergy/sensitivity or any hypersensitivity to components of study drugs or their formulation
- ✓ Current or history of decompensated liver disease (including but not limited to encephalopathy, variceal bleeding, or ascites) prior to study entry

- ✓ History of hepatocellular carcinoma (HCC)
- ✓ Any history of active Hepatitis B or positive HBsAg test
- ✓ Platelet count < 150,000/mm³
- ✓ HCV RNA undetectable
- ✓ History of clinically significant abnormalities or co-morbidities that make the subject an unsuitable candidate for this study, in the opinion of the investigator.
- ✓ Women of childbearing potential that are not practicing at least one specified method of birth control (refer to Section 5.2) that is effective from Study Day 1 through at least 30 days after the last dose of study drug.
- ✓ Subject is currently taking any of the following prohibited medications:
 - Red yeast rice (monacolin K), St. John's Wort
 - Carbamazepine, Dabigatran, efavirenz, phenytoin, pentobarbital, phenobarbital, primidone, rifabutin, rifampin
- ✓ Subject is not able or willing to safely discontinue the prohibited medications or supplements listed below at least 14 days prior to the first dose of GLE/PIB:
 - Some HMG-CoA reductase inhibitors (including atorvastatin, lovastatin, or simvastatin) should not be taken with the study drug. Subjects receiving these statins should either (a) switch to pravastatin or rosuvastatin at least 14 days or 10 half-lives (whichever is longer) prior to the first dose of study drug or (b) may interrupt statin therapy throughout the treatment period beginning at least 14 days or 10 half-lives (whichever is longer) prior to the first dose of study drug and until 14 days after the last dose of study drug, based on investigator's judgment. If switching to or continuing pravastatin or rosuvastatin, it is recommended to reduce the pravastatin dose by 50% or limit the rosuvastatin dose to 5 mg QD when taking with the study drug.
 - Astemizole, cisapride, terfenadine
 - Ethinyl estradiol

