2.2 Clinical Hypothesis

An HCV test and treat strategy, defined as immediate offer of and access to HCV treatment after testing HCV positive enhanced by peer support, will be associated with higher rates of HCV treatment initiation and cure compared to standard of care (SOC) referral to off-site HCV treatment.

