4.1 Overall Study Design and Plan

This is an open label, multicenter, phase IV randomized trial to assess the effectiveness of an HCV test and treat strategy with peer enhancement compared to standard of care referral.

The study is designed to enroll approximately 124 HCV infected subjects at 4 drug treatment program sites in the US and 1 drug treatment program site in Canada.

We will also characterize the processes of implementation of peer supported on site HCV treatment at the drug treatment clinics including adoption, fidelity, drug treatment clinic staff acceptability, and drug treatment clinic workflow integration and congruence.

Figure 2: Study Schema

* Study laboratory testing (HCV RNA, CBC, CMP, HBsAg, BHcG) may be collected prior to randomization.

Test and treat strategy with peer support: Consistent with the approach in substance use self-help groups such as narcotics anonymous, the intervention will include support for HCV treatment initiation and completion from true peers (PWUD who have previously engaged in HCV treatment).

Peer Mentor selection and training: Many OTPs utilize peers as an element of substance use recovery. Each site will identify individuals with a history of drug use who have been treated for HCV and demonstrate good communication and interpersonal skills to serve as peers. These individuals may be referred to study staff by OTP staff. They will then be offered participation in the study and be consented to participate in the study as peers, and will undergo a tailored validated training (up to 5 hours) developed and successfully utilized in the CHAMPS trial¹⁵. Trainings will include in-depth discussions of HCV, HCV treatment and prevention of reinfection and skill development such as effective mentoring, active listening skills, facilitation, the importance of confidentiality, and harm reduction including overdose prevention. These trainings are divided into 5 modules which can be watched independently by peers. Modules are designed to be engaging with activities which the peer will complete during the module and then discuss with site research assistants during check-in sessions. Peers will be assessed to ensure they have mastered required competencies to function effectively as a peer prior to being permitted to serve in this role.

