4.2.9 Study Arms

Intervention – Test and Treat strategy: This will consist of a meeting (in person, by phone or over video) with a trained peer mentor who will meet with the study participant after randomization to communicate information about HCV in a manner that takes into account an understanding of experiences with HCV and care access faced by people who use drugs, the potential harms of untreated HCV and the benefits of HCV treatment.

Peer Training, Monitoring, and Quality Assurance. Peers will receive training modelled on our previous experience training peers for HCV treatment support. The training will be provided as modules. Topics to be addressed in the modules are: 1) Power of peer mentoring and key values including confidentiality and respect for all persons; 2) Tools for effective communication; 3) HCV disease and substance use disorder including importance of adherence to medications/visits; 4) Self-care in the peer-mentor role; 5) review of patient tracking tools. Peers will also have an individual training session. Individual sessions will prepare the peer for their peer support role including building communication skills to enhance conversations to support HCV care engagement. Peers will be trained to improve their communication skills with a focus on: 1) providing accurate information; 2) working with patients on goal setting for HCV treatment adherence; and 3) identifying barriers to retention in care. We will ensure peers have demonstrated competency in all of their tasks through knowledge and performance assessments as judged through role-plays.

Peer support and care coordination tasks. Peers will be responsible for maintaining contact with patients in the test and treat arm. They will also complete adherence and food use with medication surveys at weekly contacts. He or she will also communicate the need to return for results of follow up testing and follow through with recommended treatment. The Peer will also communicate to the patient the expected timing of follow up appointments at the drug treatment center and will offer support for the duration of HCV treatment. Up to 15 peers will be enrolled in this study.

The treatment initiation visit at the drug treatment center will depend on the standard amount of time it takes to get results of laboratory testing back to the drug treatment center site. We expect this to be 3-5 days.

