The peer will contact the patient 2 days before and the day before the scheduled appointment to remind that participant about the appointment.

Peers will have a standard protocol for at least weekly phone contact with participants through post-treatment week 12, and will be available to answer participant questions as needed. Peers will maintain a log of peer contact, which will be submitted to research program staff weekly.

Peers will have access to drug treatment clinic staff for support with trouble shooting any arising matters.

Peers will submit weekly logs of participant contact to the research program coordinator and meet as a group (both peers and research program coordinator at each site, either virtually or in person) to review best practices and address any issues or questions related to effective performance as a peer.

If the participant does not want to work with the assigned peer, they can choose not to receive peer services.

HCV treatment initiation. At the treatment initiation visit, if still eligible for the study after all Day 0 results are available (detectable HCV RNA, platelet count >150,000, not pregnant) the patient will be offered immediate initiation of HCV treatment.

HCV treatment will be initiated at the drug treatment center. Participants will be provided a 4-week supply of glecaprevir/pibrentasvir (GLE/PIB) combination. For patients who report living and other situations that pose barriers to safe storage of a 4-week supply of medications, individual drug treatment centers will develop processes for providing GLE/PIB in quantities that can be safely stored by the participant.

At the treatment initiation visit, participants will be given a follow up appointment for 8 weeks after treatment initiation (expected end of treatment) with designated drug treatment center staff.

Standard of Care Referral to Offsite Location: Participants randomized to standard of care arm will be referred to an offsite HCV treatment site.

Using a signed release of medical information form, research staff will follow up with the referral site to see if the patient scheduled and subsequently attended an appointment and collect information on subsequent progress along the HCV care continuum.

If the patient is confirmed to have scheduled the appointment, study staff will contact the evaluating physician to make them aware that the study may provide GLE/PIB for HCV treatment.

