Participants in the standard of care arm who do not initiate HCV treatment within 6 months (24 weeks) after randomization and still meet study eligibility criteria upon rescreen will be offered HCV treatment at the OTP site via rollover to the Intervention Arm.

Any participant that does not clear HCV infection will be linked to repeat HCV treatment and care at an offsite HCV treatment location through standard of care. There are approved regimens available to treat patients who do not achieve cure with first line treatment.

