APPENDIX A. SCHEDULE OF EVENTS (ALL PARTICIPANTS)

	Recruitment Screen	Day 0	Treatment Day 1	Treatment Week 4	End of Treatment -0d/+30d	Post-Treatment Week 12 -14d/+30d	Post-Treatment Week 24 -14d/+30d	Post-Treatment Week 36 -14d/+30d	Early D/C Visit
Eligibility Review ^a	X	X							
Vital Signs ^b		X							
Demographics		X							
Medical History		X							
Concomitant Medications ^c		X			X				
Randomization		X							
Referral to HCV Treatment (SOC Arm Only)		X							
AE/SAE Collection ^d			→	→	→				
Laboratory Testing									
HBsAg		X							
Pregnancy Test ^e		X							
CBC ^f		X							
HCV RNA ^g		X			X	X		X	X
CMP		X			X	X			X
Urine Toxicology Screen		X			X	X	X	X	
Dried Blood Spot		X			X	X	X	X	X
Surveys/Questionnaires									
Study Survey		X			X	X	X	X	
PRO/QOL Measures		X			X	X	X	X	
Intervention Arm Only									
Peer Contact ^h		X	→	→	→	→			X
Study Drug Dispensation ⁱ			X	X					

^aIncluding documentation of HCV infection (antibody) and treatment history.

^bIncluding height, weight, temperature, pulse, respiratory rate, and blood pressure.

^cAll medication (including supplements and over-the-counter) will be collected.

^dAE/SAE collection starts with initiation of DAAs, continues through 30 days after last DAA dose.

^eFor all participants of childbearing potential. Urine or serum test.

^fWith or without differential.

^gCLIA certified.

^hPeer contact to occur weekly and as needed between visits until SVR 12. Contact can be in-person, via phone, or video.

ⁱStudy drug can be dispensed in smaller amounts more frequently if participant is unable to maintain 4-week supply at home.

APPENDIX B. SCHEDULE OF EVENTS (PARTICIPANTS WHO DO NOT START HCV TREATMENT BY WEEK 12 AFTER RANDOMIZATION IN EITHER ARM)

For participants who have not initiated treatment by Week 12 after randomization, complete the following.

	Week 12 after randomization -14d/+30d	Week 24 after randomization -14d/+30d	Week 36 after randomization -14d/+30d	Week 56 after randomization -14d/+30d
Laboratory Testing				
Urine Toxicology Screen	X	X	X	X
Dried Blood Spot	X	X	X	X
HCV RNA ^e		X		X
Surveys/Questionnaires				
Study Survey	X	X	X	X
PRO/QOL Measures	X	X	X	X
Rescreen for SOC Participants to Rollover to Intervention Arm				
Eligibility Review		X		
Vital Signs ^a		X		
Concomitant Medications ^b		X		
HBsAg		X		
Pregnancy Test ^c		X		
CBC ^d		X		
CMP		X		
Peer Contact ^f		→		

^aIncluding height, weight, temperature, pulse, respiratory rate, and blood pressure.

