^bAll medication (including supplements and over-the-counter) will be collected.

^cFor all participants of childbearing potential. Urine or serum test.

^dWith or without differential.

^eCLIA certified.

^fParticipant will meet with peer on date of rescreen. If participant is still eligible for rollover to Intervention Arm after rescreening labs result, peer contact to occur weekly and as needed between visits until SVR 12. Contact can be in-person, via phone, or video.

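### No rule limits the age of the pregnancy test that clears a first on-site dose, so a participant of childbearing potential whose start is delayed could be dosed on an old negative result

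*Combined protocol and SAP*

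**What the plan says.** - **Eligibility (5.1).** The inclusion criterion for participants of childbearing potential is a "Negative pregnancy test at screening or at the day of treatment initiation". The two occasions are alternatives, and no maximum interval to the first dose is given.
- **Clearance for the first dose (4.2.9, HCV treatment initiation).** Treatment is offered at the initiation visit "if still eligible for the study after all Day 0 results are available". The section lists not being pregnant among the conditions, but it names no repeat test.
- **Timing (4.2.9).** The initiation visit depends on laboratory turnaround: "We expect this to be 3-5 days".
- **Earliest date of the test (4.1, note to Figure 2).** "Study laboratory testing (HCV RNA, CBC, CMP, HBsAg, BHcG) may be collected prior to randomization", so the clearing test may predate Day 0.
- **Schedule (Appendix A).** The pregnancy test is marked at Day 0 and nowhere else. Treatment Day 1 has drug dispensation but no pregnancy test.
- **Untreated participants (Appendix B).** Those in either arm who have not started by Week 12 are followed at Weeks 12, 24, 36 and 56. The only pregnancy test is at Week 24, in the block headed "Rescreen for SOC Participants to Rollover to Intervention Arm".
- **Rollover (4.2.9).** Standard-of-care participants untreated at 24 weeks who "still meet study eligibility criteria upon rescreen will be offered HCV treatment at the OTP site".

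**The concern.** Taken together, these provisions fix when the pregnancy test is first done but not how old it may be when drug is given. If a test-and-treat participant misses or postpones the initiation visit, the written conditions can still be met by the Day 0 result. A pregnancy that began after Day 0 and has not been recognised would not be found by any scheduled test before dosing.

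What is at stake is the order of events. Section 6.2.4 provides for a discussion of benefit and risk with a participant found to be pregnant during treatment, and allows drug to continue where benefit outweighs risk. With an old test, that discussion could come after the first dose when it could have come before. The estimate of the treatment effect is not at stake.

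**Working it through.** The plan gives no limit of its own to reproduce. The check is a comparison of the relevant sections plus calendar arithmetic.

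**Step 1. Is a same-day test required?** No. In 5.1 it is one of two alternatives, 4.2.9 refers to Day 0 results, and Appendix A has no mark at Treatment Day 1. The three places agree with each other.

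**Step 2. Is the gap from test to dose capped elsewhere?** No. The 3-5 days in 4.2.9 describe laboratory turnaround. The 12 weeks in 3.2 define the primary endpoint and do not close the offer. The time-to-initiation endpoint in 3.3 has no cut-off, and Appendix B follows untreated participants of both arms to Week 56. No text says that a test-and-treat participant may no longer start on site after some date.

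**Step 3. How old could the test be?** Age at first dose is at least 7 × (weeks from randomization to first dose), because the test is taken on Day 0 or earlier.

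| First dose | Minimum age of a Day 0 test |
|---|---|
| Expected visit | 3-5 days |
| Week 12 | 12 × 7 = 84 days |
| Week 24 | 24 × 7 = 168 days |

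Any result drawn before randomization would be older still.

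**Step 4. Does a scheduled repeat intervene?** The Week 24 visit has a window of -14 to +30 days, so it falls between day 168 - 14 = 154 and day 168 + 30 = 198. Neither arm has a scheduled pregnancy test between Day 0 and day 154. From day 154 the repeat is headed for standard-of-care rollover only.

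**Step 5. What does the protocol do for the late on-site start that it describes?** It retests. Footnote f of Appendix B makes the repeat results the condition for going ahead: "If participant is still eligible for rollover to Intervention Arm after rescreening labs result". A test-and-treat participant starting equally late, with the same drug at the same site, has no corresponding written check.

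**The case against.** The strongest reply is that the scenario is not in the plan. The strategy is defined in 2.2 as "immediate offer of and access to HCV treatment after testing HCV positive", and 4.2.9 places the offer at one initiation visit timed by laboratory turnaround. Apart from the rescreen block, Appendix B is follow-up and does not show a continuing offer to the test-and-treat arm. This stands in part: starts after Week 12 in that arm are inferred from the absence of a cut-off. A reader might infer that the protocol plans or expects such starts, but no text says so. Week 12 also has no particular meaning for pregnancy. It is the endpoint window, used here only as an example of a long delay.

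The second reply is that safeguards exist. Pregnancy is an exclusion, and so is considering becoming pregnant (5.1). Contraception is required throughout the study (5.2), and participants are cautioned against pregnancy (4.2.5). The initiation visit lists not being pregnant as a condition, and 5.1 already lets a site test on the day. Sections 5.5 and 6.2.4 deal with pregnancy on treatment. These lower the risk, and they mean that an old test is permitted but not directed. None of them, however, requires a test that would detect an unrecognised pregnancy before a delayed first dose.

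The third reply is that the numbers must be very small. That stands. The documents do not give the proportion of childbearing potential, the frequency of delayed starts or a pregnancy rate, so no useful count can be derived.

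**Conclusion.** The gap is real but minor. A negative screening test is sufficient under 5.1, the on-site start is cleared on Day 0 results under 4.2.9, and no test is scheduled at Treatment Day 1. A delayed starter of childbearing potential could therefore be dosed on a test weeks old, or 84 days or more for a start after Week 12. This rests on two readings: that the 3-5 days are not a limit, and that the on-site offer stays open because nothing closes it.

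The documents do not support a stronger conclusion. A reader might infer that participants are likely to be dosed while pregnant, but the plan gives no basis for any number, and it may be zero. A reader might also infer that the standard-of-care heading on the Week 24 block causes the problem. It does not, because that visit falls on days 154-198 and cannot account for old tests before then. The primary endpoint, sample size and power are unaffected. This is an inexpensive safety improvement that the sponsor could make.

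**What to change.** In 5.1, 4.2.9 and the Treatment Day 1 column of Appendix A, require a negative point-of-care urine pregnancy test on the day of the first on-site dose, for participants of childbearing potential in either arm, whenever the start falls later than the expected laboratory turnaround. A workable trigger is a last test more than 7 days old, which leaves 7 - 5 = 2 days beyond the upper end of the expected 3-5 days. The 7 days are an example, and the clinical team should set the limit. Applying the rule to both arms also covers a rollover participant whose first dose is delayed after the Week 24 retest, since no limit is set there either.

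The cost is one clause in 5.1, one sentence in 4.2.9, one conditional mark in Appendix A, and one dipstick per affected participant. The dipstick is already a protocol test (4.2.5) and adds no laboratory wait. Drug dispensation is already an in-person activity (4.2.12), so no extra visit is needed. Participants who start within the expected window are unaffected.
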